3.5. Adjustment for multiplicity

No adjustment for multiplicity will be made.

3.6. Interim analyses

No interim analyses were done or planned.

3.7. Handling of missing data

If less than 10% of data is missing, the primary analysis will be conducted using the participants with available data for each outcome. However, if there are >10% missing data in the primary or secondary outcomes, we will conduct the analysis under a plausible assumption regarding the missingness mechanism that will be guided using expert clinical knowledge prior to observing the data, which will be determined by generating directed acyclic graphs. We suspect that the data will be recoverable (that is able to be estimated without bias from the observed data alone), and multiple imputation will be used to handle the missing data in all

outcomes. Imputations will be generated using chained equations, also known as fully conditional specification, with 50 imputed datasets and 10 iterations between each imputation. Ideally this would be conducted using a single regression model for all outcomes, although it may be necessary to impute incomplete outcomes using separate models. Imputation will be carried out separately by arm, to ensure that any treatment effects are maintained. Baseline characteristics as well as any variables that are predictors of missingness and/or associated with the incomplete outcomes will be included as auxiliary variables in the imputation model. Estimates of interest will be obtained using Rubin's rules, and will be reported with 95% confidence intervals and *p*-values.

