2.6 Sample size

For the primary research outcome, a sample size of 120 index cases per arm will provide 80% power. We anticipate that the attack rate for within household transmission will be approximately 85% in the control arm and 75% in the intervention arm. Under these assumptions, in a cluster randomised trial with a binary outcome, assuming an intracluster correlation coefficient of 0.2, an alpha of 0.05 (two sided), and assuming 3 additional household members (in addition to the index case) we have 80% power to detect a reduction in transmission to household contacts. The requisite sample size is then 120 index cases and 360 household contacts per arm. Allowing for 10% loss to follow-up this is increased to 134 index cases (households) per arm, approximately 536 persons per arm. We plan to enroll 268 households and approximately 1072 individuals.

If the household size is 2 additional people, rather than 3, and with all other assumptions the same, we would require 334 households and approximately 1002 individuals. The target sample size for the primary outcome is 1100 individuals enrolled.

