The analysis will follow the intention to treat principle, but only some households will be eligible for this objective. A household will be eligible if there is at least one participant in the household who tested positive to SARS-CoV-2 by PCR on Day 1 and one participant who tested negative to SARS-CoV-2 by PCR on Day 1, using the health care provider collected swab. It does not matter whether it was the index case or another household member who tested positive. Households where all participants test positive or where all participants test negative will not be eligible for this analysis.

Treatment arms will be compared using generalised linear mixed models (GLM) with infection status as the binary outcome, adjusting for stratification factors (time from positive test to randomisation, whether the index case is a child < 5 years), participant age, inhaled steroid use at baseline, days since symptom onset at randomisation, whether there are children in the household and household size (referred to as the defined baseline covariate set, see Section 3.9), with household as random effect to take the clustering by household into account. Both relative and absolute differences in proportions will be reported with 95% confidence intervals.

Relative differences (risk ratios) between the treatment arms will be calculated using a Poisson regression with robust standard errors in Stata as follows:

xtpoisson outcome i.arm baseline_covariates, re vce(robust) irr

Absolute differences (risk difference) between the treatment arms will be calculated in Stata as follows using a mixed effects GLM with random intercepts: megIm outcome i.arm baseline_covariates || household:, family(bin) link(logit)

The margins statement will be used to compute the risk difference by subtracting the probability of the outcome in the control arm from the probability in the treatment arm margins i.arm, atmeans post lincom _b[1.arm] - _b[0.arm]

Both these models are fairly complicated models to fit and might not converge if sparse data is encountered, given all the baseline covariates included. If the models do not converge, the following strategies will be tried:

- Exclude some of the baseline covariates especially binary covariates, covariates with sparse categories, or covariates with little variability
- Or, fit the following simpler models

Relative differences (risk ratios) between the treatment arms will be calculated in Stata as follows using robust standard errors:

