5.2. Sensitivity analyses

Four sensitivity analyses are planned:

- 1. The analysis described above will be repeated using multiple imputation, if more than 10% of outcome data is missing.
- 2. The analysis described above willbe repeated without the covariates participant age, inhaled steroid use at baseline, days since symptom onset at randomisation, whether there are children in the household and household size.
- 3. The algorithm to determine SARS-CoV-2 infection will be changed by deeming all inconclusive results (including on Day 0) to be positive, using only healthcare provider collected swabs.
- 4. The algorithm to determine SARS-CoV-2 infection will be changed by deeming all inconclusive results (including on Day 0) to be negative, using only healthcare provider collected swabs.

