5.3. Supplementary analyses

We define a supplementary estimand, through handing the intercurrent event of not taking study drug differently.

Supplementary estimand

Population: Household contacts who test negative for SARS CoV-2 on day 1 (baseline) PCR testing using the health care provider swabs

Treatment: Unfractionated intranasal heparin 1400u each nostril (as heparin solution 5,000u/ml, 140microL/actuation, TWO actuations each nostril) THREE times daily via a plastic nasal inhalator device or saline control

Outcome: Testing positive for SARS-CoV-2 by PCR on any of three health care provider collected swabs at days 3, 5 and 10 while participant and index case do not discontinue treatment due to adverse events. The algorithm to determine SARS-CoV-2 positivity is described in detail in Section 3.8. If one of the post-baseline swabs is missing, but all observed swabs were negative, the participant will be regarded to be negative. If more than one post-baseline swab is missing and the observed swabs were all negative, the outcome will be regarded to be missing.

Summary measure: Both relative (risk ratio) and absolute differences (risk difference) in proportions will be reported with 95% confidence intervals

Potential intercurrent events:

Index case in the household not taking study drug. This is defined as compliance <90% Participant (this household member) not taking study drug. This is defined as compliance <90% Either participant (this household member) or index case stop treatment due to adverse event Participant hospitalisation during first 10 days (removed from household) Participant received an anti-viral

Strategy for handling intercurrent event:

Index case in the household not taking study drug. This is defined as compliance <90%: This intercurrent event will be handled following the hypothetical strategy. For index cases who used <90% of study drugs we will set all SARS-CoV2 infections observed in the household to missing. We will use multiple imputation to impute these outcomes.

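### The imputation model in SAP 3.7 takes no account of household, so standard errors in the imputed analyses come out modestly too small

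*SAP*

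**What the plan says.** Section 3.7 sets out the imputation in some detail: "Imputations will be generated using chained equations, also known as fully conditional specification, with 50 imputed datasets and 10 iterations between each imputation". It continues: "Imputation will be carried out separately by arm, to ensure that any treatment effects are maintained". On predictors: "Baseline characteristics as well as any variables that are predictors of missingness and/or associated with the incomplete outcomes will be included as auxiliary variables". On pooling: "Estimates of interest will be obtained using Rubin's rules". Household does not appear as a random effect, a fixed effect or a source of predictors built from other members' results. Sections 5.2 and 5.3, which call on this imputation, do not add it.

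Elsewhere the plan rests on household. Section 2.5 randomises by household. Section 2.6 sizes the trial "assuming an intracluster correlation coefficient of 0.2". Section 5.1 fits the primary model "with household as random effect to take the clustering by household into account".

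Imputation enters in two places. Above 10% missing outcome data, 3.7 reads as making it the analysis, whereas 5.2 lists it as a sensitivity analysis: "The analysis described above will be repeated using multiple imputation, if more than 10% of outcome data is missing". Table 8 likewise gives it separate rows after the complete-case rows. In the supplementary estimand of 5.3, the plan says: "For index cases who used <90% of study drugs we will set all SARS-CoV2 infections observed in the household to missing", and those outcomes are then imputed. That analysis is run only if more than 7% of participants had the intercurrent events. Section 6.1 carries the supplementary analysis over to measures 1.1 to 1.3.

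**The concern.** An imputation model should be at least as rich as the analysis model it feeds. The plan applies this principle to treatment, which is why it imputes by arm, but not to household.

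If household is ignored, two things happen. Imputed outcomes in one household are drawn independently, so the completed data are less correlated than the real data. The imputation parameters are also drawn as if every person were an independent observation, so the between-imputation variance is too small. A household random effect or cluster-robust variance applied afterwards cannot restore correlation that the imputation removed. The result is intervals that are too narrow and a false-positive rate somewhat above nominal in the imputed analyses.

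**Working it through.** **Inputs.** From 2.6: risks 85% and 75%, ICC ρ = 0.2, m = 3 contacts per household, 120 households (360 contacts) per arm, 10% loss; the alternative is m = 2. From 3.7: 50 imputations, by arm, no household term. Assumed, because the plan gives no expected share: the fraction f of individual outcomes missing at random, or the fraction h of whole households imputed.

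**The plan's own figure.** Two-proportion sample size, 80% power, two-sided 0.05:

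(1.96·√(2·0.80·0.20) + 0.8416·√(0.85·0.15 + 0.75·0.25))² / 0.10² = 250 per arm.

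- m = 3: design effect 1 + 2·0.2 = 1.4, and 250·1.4/3 = 117 households per arm. The plan states 120, which gives 81.1% power. 120/0.9 = 134 per arm, 268 in total.
- m = 2: 250·1.2/2 = 150 per arm. 150/0.9 = 167 per arm, 334 in total.

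The plan's figures therefore reproduce (117 against 120), and clustering is material to them.

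**Dilution of the ICC.** A pair in the same household keeps its correlation only if both members are observed, so the ICC after household-blind imputation is about ρ(1−f)². For f = 10%, 15%, 20% and 30% this gives 0.162, 0.145, 0.128 and 0.098. Simulation gave 0.155, 0.141, 0.123 and 0.096.

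**Standard error, scattered missingness.** Take n contacts per arm and a large number of imputations, and express variances in units of p(1−p)/n.

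- True variance of the arm mean: 1/(1−f) + (m−1)ρ.
- Rubin total: within 1 + (m−1)ρ(1−f)², plus between f/(1−f), which sums to 1/(1−f) + (m−1)ρ(1−f)².
- SE ratio: the square root of the second over the first.

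For m = 3:

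- f = 10%: √[(1.111 + 0.324)/(1.111 + 0.4)] = 0.975
- f = 12%: √[(1.136 + 0.310)/(1.136 + 0.4)] = 0.970
- f = 30%: √[(1.429 + 0.196)/(1.429 + 0.4)] = 0.943

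**Standard error, whole households imputed.** True variance is [1 + (m−1)ρ]/(1−h). The Rubin total is 1/(1−h) + (m−1)ρ(1−h). The ratio is √{[1 + (m−1)ρ(1−h)²]/[1 + (m−1)ρ]}.

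- m = 3, h = 20%: √(1.256/1.4) = 0.947
- m = 3, h = 30%: √(1.196/1.4) = 0.924
- m = 2, h = 20%: √(1.128/1.2) = 0.970
- m = 2, h = 30%: √(1.098/1.2) = 0.957

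For m = 2 and f = 10% scattered: √[(1.111 + 0.162)/(1.111 + 0.2)] = 0.985.

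**Simulation check.** Beta-binomial households, imputation by arm, cluster-robust risk difference without covariates, Rubin's rules, 20 imputations, 1000 to 3000 trials per setting. Mean SE with m = 3 and 120 households per arm:

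| Missing | Without household | With household | Shortfall |
|---|---|---|---|
| 10% scattered | 0.0355 | 0.0363 | 2.2% |
| 15% scattered | 0.0360 | 0.0371 | 3.0% |
| 20% scattered | 0.0363 | 0.0378 | 4.0% |
| 30% scattered | 0.0379 | 0.0398 | 4.8% |
| 20% of households + 5% of individuals | 0.0377 | 0.0399 | 5.5% |
| 30% of households + 5% of individuals | 0.0395 | 0.0429 | 7.9% |

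Coverage in the last two rows was 93.0% and 92.6% without household, against 94.3% and 94.6% with it. At 10% scattered it was 94.2% against 94.9%. The Monte Carlo error of a coverage figure near 95% with 1500 trials is √(0.95·0.05/1500) = 0.6 points.

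A separate run with the planned 50 imputations and 3000 trials, set against a complete-case control, gave SE ratios of 0.971 (12% scattered), 0.949 (20% of households) and 0.926 (30% of households). Coverage was 94.0%, 92.7% and 92.5%, against 94.8%, 94.2% and 95.0% for complete cases. With 2 contacts per household (150 per arm) the three ratios were 0.984, 0.970 and 0.959.

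**The case against.** **Silence is not exclusion.** A reader might infer that the plan rules household out. It does not. Baseline characteristics in 4.2 include household size, household type and numbers of bedrooms and bathrooms, which may carry part of the between-household variation. The clause on variables associated with the outcomes could be stretched to other members' infection results. This stands in part. But household-level covariates do not carry household membership, and the clause does not name other members' results, so two analysts could follow 3.7 and obtain different intervals.

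**The primary interval may be untouched.** A reader of 3.7 alone might infer that the flaw reaches the primary confidence interval. Section 5.2 and Table 8 place imputation among the sensitivity analyses, so the documents do not settle this. At or below 10% missing, and outside 5.3, nothing is affected.

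**The size is small and partly assumed.** This stands. Comparing imputed standard errors with the empirical spread of estimates, without a control, can suggest a shortfall near 10%. That comparison has Monte Carlo error of about 1.8% with 1500 trials, and the controlled comparison gives 5–8% at most in the settings tried at ICC 0.2. The primary analysis uses only members negative on day 1, so clusters may be smaller than 3. The outcome rule in 5.1 also counts one missing swab with the others negative as negative, so fewer outcomes than swabs are missing. Both reduce the effect.

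**Conclusion.** The point holds at a modest size. Followed as written, 3.7 imputes household members as independent given covariates, which conflicts with the plan's randomisation, sample size and analysis model. At ICC 0.2 and 3 contacts per household, standard errors are about 2–3% too small near the 10% trigger with scattered missingness. They are about 5–8% too small if 20–30% of whole households are imputed, where simulated coverage is about 92–93%. With 2 contacts the shortfall is about 1–4%.

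These figures assume outcomes missing completely at random and no covariates, and the missing shares are not from the plan. I read the household rule in 5.3 as setting every member's outcome to missing. The effect grows with the ICC: at an assumed 0.5 with 30% scattered missing, it is 0.0412 against 0.0451, or 9%.

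The documents do not support the broader claim that the trial's main result would have invalid intervals. The consequence is confined to analyses that use imputation, and it is greatest in the supplementary estimand.

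**What to change.** Add a sentence to 3.7, and refer to it from 5.3: imputation will be done separately by arm and will account for household, either by a household random intercept (multilevel imputation) or by imputing in household-wide format. For scattered missingness, the minimum is to include other members' infection results as predictors. That is not enough where a whole household is imputed, because no member's result is then left to condition on, so 5.3 needs the multilevel or household-wide model. The same edit should settle whether the imputed analysis is the main analysis above 10% missing (3.7) or a sensitivity analysis (5.2, Table 8).

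The cost is a short SAP amendment, moderate extra programming (slower multilevel imputation or a wide data layout with unequal household sizes) and slightly wider intervals. Design and data collection do not change.

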3.8. Assigning SARS CoV-2 infection status at day 1 and for all outcomes

The following algorithm will be used to determine whether a participant is regarded as positive or negative for SARS CoV-2. In general, only the health care provider collected PCR result will be used to determine infection status. The exception would be when the result was inconclusive.

SARS CoV-2 infection at the time point will be positive if the health care provider collected PCR result is "Detected" and negative if the PCR result is "Not detected".

If the result of the healthcare provider collected swab was inconclusive the following algorithm will be followed:

The result of the self-collected Rhinomed swab collected on the same date as the inconclusive healthcare provider collected swab will determine the final result. If the result of the self-collected Rhinomed swab is "Detected" the result will be positive and if the result is "Not detected" the result will be negative.

If the self-collected Rhinomed swab was also inconclusive, or was missing, the following algorithm will be followed (using the healthcare provider collected swab):

- If the inconclusive result was followed later by a "Detected" result (for example, Inconclusive on Day 3 and Detected on Day 5) then the inconclusive result will be deemed to be positive.
- If the inconclusive result was followed later by a "Not detected" result, then the inconclusive result will be deemed to be negative.
- If the inconclusive result was the last available result, then the inconclusive result will be deemed to be negative.

This algorithm will be used to determine both the primary endpoint (positive on any of Day 3, 5 or 10) and all secondary endpoints related to SARS-CoV-2 positivity.

For the primary objective only, the following two sensitivity analyses will also be done:

Sensitivity analysis 1: Only healthcare provider collected swabs will be used. If the result is inconclusive, it will be regarded as positive.

Sensitivity analysis 2: Only healthcare provider collected swabs will be used. If the result is inconclusive, it will be regarded as negative.

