2.7 Study procedures

When a participant is confirmed to be SARS-CoV-2 positive all consenting household members are enrolled and randomised to the same treatment arm. All consenting household members 5 years of age and older will be given the same study treatment. Treatment is 10 days and follow up for primary outcome is 10 days. Follow up for some secondary outcomes are 28 days and outcomes related to long COVID is 6 and 12 months post randomisation.

Daily communication via SMS, online or phone will be conducted by a research team member who will be trained in standard operating procedures as per trial manual. Paediatric or adult swabs (Rhinomed) will be provided to all participants with detailed instructions for self-collection and storage until collected by a research team member. Health care provider collected PCR nasopharyngeal swabs will be collected from all participants prior to commencement of study medication and on day 3, 5 and 10 (+/- 1 day for all time points).

Phone call follow up at day 14 and 28 by a research team member will assess which participants became symptomatic after the initial treatment period and whether participants required hospitalisation during that time. Detailed medical information as to reasons for hospital admission will be sought to confirm if admission was related to COVID-19 infection or for alternative reasons. Research team members will be trained specifically in questions to ask according to trial manual, which will include an escalation process if a research team member believes that additional clinical care is required for the participant or family member.

Telemedicine follow up at day 180 +/- 10 days and day 365 +/- 10 days to ascertain any evidence of long COVID neurological symptoms.

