5. ANALYSIS OF THE PRIMARY OUTCOME(S)

5.1. Main analysis

The primary outcome will be the number (and proportion) of household members swab negative on day 1 (study timepoint called baseline) testing positive for SARS-CoV-2 by PCR on either of three routine nasopharyngeal swabs on day 3, 5 and 10 after enrolment.

Primary estimand

Population: Household members (including children < 5 years) who test negative for SARS CoV-2 on day 1 (baseline) PCR testing using the health care provider swabs

Treatment: Initially randomised intervention to unfractionated intranasal heparin 1400u each nostril (as heparin solution 5,000u/ml, 140microL/actuation, TWO actuations each nostril) THREE times daily via a plastic nasal inhalator device or saline control and any subsequent deviations to the per protocol use of the intervention over 10 days

Outcome: Testing positive for SARS-CoV-2 by PCR on any of three health care provider collected swabs at days 3, 5 and 10. The algorithm to determine SARS-CoV-2 positivity is described in detail in Section 3.8. If one of the post-baseline swabs is missing, but all observed swabs were negative, the participant will be regarded to be negative. If more than one post-baseline swab is missing and the observed swabs were all negative, the outcome will be regarded to be missing.

Summary measure: Both relative (risk ratio) and absolute differences (risk difference) in proportions will be reported with 95% confidence intervals

Potential intercurrent events:

Index case in the household not taking study drug. This is defined as compliance <90% Participant (this household member) not taking study drug. This is defined as compliance <90% Either participant (this household member) or index case stop treatment due to adverse event Participant hospitalisation during first 10 days (removed from household) Participant received an anti-viral

Strategy for handling intercurrent event:

In the primary analysis all intercurrent events will be handled through the treatment policy strategy, which means that the intercurrent events will be ignored.

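### A self-collected swab decides infection status when the provider swab is inconclusive but is not used when the provider swab is missing, so a recorded 'Detected' result can be scored as uninfected in the primary outcome

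*SAP*

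**What the plan says.** Section 3.8 sets the general rule: "In general, only the health care provider collected PCR result will be used to determine infection status". It then makes one exception: "The exception would be when the result was inconclusive". In that case "The result of the self-collected Rhinomed swab collected on the same date as the inconclusive healthcare provider collected swab will determine the final result". The same section treats inconclusive and missing as different states, but only for the self-swab: "If the self-collected Rhinomed swab was also inconclusive, or was missing, the following algorithm will be followed". It says nothing about a provider swab that was not taken. Its scope is wide and takes in every positivity outcome: "This algorithm will be used to determine both the primary endpoint (positive on any of Day 3, 5 or 10) and all secondary endpoints".

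Section 5.1 defines the primary outcome as "Testing positive for SARS-CoV-2 by PCR on any of three health care provider collected swabs at days 3, 5 and 10". On gaps it says: "If one of the post-baseline swabs is missing, but all observed swabs were negative, the participant will be regarded to be negative". With two or more swabs missing and the observed ones negative, it sets the outcome to missing.

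Section 2.7 indicates that self-swabs should exist: "swabs (Rhinomed) will be provided to all participants with detailed instructions for self-collection and storage". The team then collects them. Section 2.8, explaining why references to daily swabs were removed, says that only provider swabs are used. That does not match the fallback in 3.8.

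**The concern.** For an inconclusive provider swab, 3.8 trusts the self-swab enough to let it settle the result. For a provider swab that was never taken, the plan has less information, yet it assigns a firm negative even where a 'Detected' self-swab covers the same visit. The same self-swab result thus leads to opposite classifications, depending only on why the provider result is unavailable.

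At stake is the primary outcome. Infections already on record could be counted as non-infections. That lowers the measured risk in both arms, shrinks the absolute difference and costs some power. If the missed share differed between arms, it would also distort the risk ratio.

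**Working it through.** **1. The rules side by side.** Provider results are given for days 3/5/10, each with a 'Detected' self-swab at the gap.

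| Provider swabs | Gap is inconclusive (3.8) | Gap is missing (3.8 with 5.1) |
|---|---|---|
| gap / negative / negative | Positive | Negative |
| negative / gap / negative | Positive | Negative |
| negative / negative / gap | Positive | Negative |

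With two provider swabs missing and the third negative, the outcome is missing and the self-swab is again unused.

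**2. Whether a planned analysis would show it.** Section 5.2 lists four. Analysis 1 is multiple imputation if more than 10% of outcome data is missing; participants with one missing swab are coded negative, so they are not imputed. Analysis 2 drops covariates. Analyses 3 and 4 recode inconclusive results using provider swabs only. None reaches this case.

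**3. The plan's own figure.** Section 2.6 assumes 85% versus 75%, an intracluster correlation of 0.2, 3 contacts per household, two-sided alpha 0.05 and 80% power. The standard two-proportion formula gives 250 per arm. The design effect is 1 + (3 − 1) × 0.2 = 1.4, so 250 × 1.4 / 3 = 116.7, or 117 households per arm, within 3% of the stated 120. Inflation reproduces exactly: 120 / 0.9 = 133.3, or 134. With 360 contacts per arm the effective size is 360 / 1.4 = 257 and power is 81.1%. The sizing is sound and serves here only as the reference.

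**4. Upper bound on misclassification.** The SAP gives none of these rates, so they are assumptions:
- m, the share with exactly one missing provider swab: 5-20%
- u, the share of infected participants positive only on that swab: 5-20%
- risk: 80%, midway between 85% and 75%

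Infected but scored negative = m × 0.80 × u:
- low: 0.05 × 0.80 × 0.05 = 0.2%
- high: 0.20 × 0.80 × 0.20 = 3.2%

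This counts every error from the one-missing rule. The recoverable part is m × 0.80 × u × d, where d is the probability that a 'Detected' self-swab is on file. The SAP gives no basis for d.

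**5. Effect if the missed share s is equal in both arms.** As a share of infections, s = m × u, that is 0.25% to 4%. Observed risks are 0.85(1 − s) and 0.75(1 − s).

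| s | Risks | Risk difference | Risk ratio | Power |
|---|---|---|---|---|
| 0 | 0.850 / 0.750 | 10.0 points | 0.882 | 81.1% |
| 1% | 0.8415 / 0.7425 | 9.9 | 0.882 | 79.2% |
| 2% | 0.833 / 0.735 | 9.8 | 0.882 | 77.2% |
| 5% | 0.8075 / 0.7125 | 9.5 | 0.882 | 71.4% |

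At the 4% top of the assumed range, the risk difference is 0.816 − 0.720 = 9.6 points. The factor (1 − s) cancels in the risk ratio.

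**6. Effect if it is unequal (hypothetical).** With 2% missed in the heparin arm only: 0.850 − 0.735 = 11.5 points, risk ratio 0.865. With 2% missed in the control arm only: 0.833 − 0.750 = 8.3 points, risk ratio 0.900.

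**The case against.** Provider-only ascertainment is a stated and defensible choice, repeated in 3.8, 5.1 and 2.8. On that view the self-swab is a narrow tie-breaker for a specimen that exists but cannot be read, matched to it by date. A missing provider swab has no date to match. This explains the rule but does not remove the inconsistency: once 3.8 lets the self-swab decide, the plan is no longer provider-only, and 2.8 contradicts it.

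The objection to a loose repair stands. The ±1 day windows in section 2.7 overlap at day 4, which belongs to both day 3 and day 5. If several self-swabs were taken around a missed visit, accepting any of them would give people who missed a visit more chances to test positive than people who attended. Any fallback therefore needs a strict date rule and one self-swab per visit.

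Two limits on the data also stand. Section 2.7 shows that self-swabs were supplied, not that they were taken when a provider visit was missed. The SAP does not name the self-swab assay; its results are reported in the same categories as the provider PCR, so PCR is a reasonable inference and not a stated fact.

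Participants with two or more missing swabs are partly covered, since imputation applies above 10% missing and self-swab results could serve as auxiliary variables.

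**Conclusion.** The inconsistency is real and follows from the text of 3.8 and 5.1. The firm false negative arises with exactly one missing provider swab, the other two negative and a 'Detected' self-swab for the missed visit. No planned analysis examines it.

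Its size is unknown. A reader might take 0.2-3.2% as the number of known positives being discarded. The documents do not support that: both rates are assumed, and the range leaves out the chance that a 'Detected' self-swab is on file, so it is an upper bound.

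A reader might also infer that the treatment comparison is biased. The documents give no reason for missed swabs to differ by arm in this double-blind, placebo-controlled trial. With equal shares the risk ratio stays at 0.882, and across the assumed range the risk difference falls from 10.0 to no lower than 9.6 points, with some loss of power. Bias in the risk ratio needs the missed share to differ by arm.

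The point merits correction because the repair is cheap and stops a recorded positive from being scored as a firm negative.

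**What to change.** In 3.8 and 5.1, state that when a post-baseline provider swab is missing, a 'Detected' self-collected swab taken on the scheduled visit date makes that time point positive. If there is none on that date, use the single self-swab nearest to it. Assign each self-swab to one visit only, which settles day 4. Do not use a 'Not detected' self-swab to fill a missing provider result in the main analysis.

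At minimum, run this as a named sensitivity analysis of the primary outcome. Keep provider-only coding in sensitivity analyses 3 and 4 of section 5.2. Reconcile the statement in 2.8 that only provider swabs are used with the fallback in 3.8.

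The cost is SAP wording and a data merge, provided the self-swab results are on file as 3.8 implies. The downside is some dependence on whether self-swabs were taken and on their accuracy, which 3.8 already accepts for inconclusive results.
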